7.1 General Considerations

7.1.1 General Methods

(1) Descriptive Statistics

Unless otherwise specified, the following descriptive statistics are given according to the variable types:

- Continuous variables will be summarized by mean, standard deviation, median, minimum and maximum.
- Category or ordinal variables will be summarized by frequency counts and percentages, where the denominator will be the number of non-missing participants in the corresponding analysis set.

(2) Decimal Places

Unless otherwise specified, the number of decimal places in the TFLs will follow the belowing rules:

- The decimal place of minimum and maximum will be the same as the maximum one of raw data, and no more than 4.
- The decimal place of mean, median, standard deviation and 95% CI are one more than the maximum decimal place of raw data, and no more than 4.
- The decimal places of percentage and rate will be 2.
- If P value ≥ 0.0001 , the decimal place will be 4, and if the P value < 0.0001 , it will be reported as "<0.0001".
- Statistics will be retained to 3 decimal places.
- The derived data will be retained to 2 decimal places.

7.1.2 Related Definitions and Derivation Rules

(1) Adverse Events Times

Occurrence time of AE (day) = Start date of AE – the corresponding vaccination date.

Duration of AE (day) = End date of AE – Start date of AE + 1.

(2) Treatment Emergent Adverse Event (TEAE)

The following rules will be used for TEAE.

- If the start date of AE is after (including) the date of the first vaccination, it will be defined as TEAE.
- If the start date of AE is before the date of first vaccination, it will be defined as non-TEAE.
- If either the start date of AE or the date of the first vaccination is missing such that it is not clear whether the AE occurred after the first vaccination, it will be defined as TEAE in all situations.

(3) Relationship of TEAE

- Related to the study vaccine means that the TEAE is "definitely related", "probably related" or "possibly related" to the study vaccine.
- Not related to the study vaccine means that the TEAE is "Not related" or "Unlikely related" to the study vaccine.

(4) Coding

Medical histories, AEs and SAEs will be coded by using the Medical Dictionary for Regulatory Activities (MedDRA) version 25.1 or later version. Prior and concomitant medications / vaccines will

be coded by using world health organization drug dictionaries 2022-Sep-1 (WHODrug_2022-Sep-1) or later version.

(5) Prior or Concomitant Medications

The following rules will be used to define prior and concomitant medications.

- If the end date of the medication is before (not including) the date of the first vaccination, it will be defined as a prior medication.
- If the start date of the medication is before (including) the date of the first vaccination and the end date of the medication is after (including) the date of the first vaccination, or the medication is still being used, or the start date of the medication is after (including) the date of the first vaccination, it will be defined as a concomitant medication.
- If either the start date of the medication or the date of the first vaccination is missing such that it is not clear whether the medication occurred after the first vaccination, it will be defined as a concomitant medication in all situations.

(6) Prior or Concomitant Vaccines

The rules of prior and concomitant vaccines definition will be the same as the rules for prior or concomitant medication above.

(7) Immunogenicity Test Results

In the analysis of immunogenicity evaluation, "< LLoQ" will be treated as 1/2 of LLoQ (Lower Limit of Qualification), and "> ULoQ" will be treated as ULoQ (Upper Limit of Qualification).

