9.3.5 Safety Analysis

Treatment-emergent adverse events (TEAEs) are defined as any AEs that occurred on or after vaccination date or worsening of existing events. AEs will be coded using the Medical Dictionary for Regulatory Activities (MedDRA), version 25.0 or later version.

TEAEs will be summarized by frequency and percentage, and tabulated by system organ class (SOC) and preferred term (PT). Serious adverse events (SAEs) will also be summarized.

The following summary tables and patient level listings will be presented for TEAE data:

- Overall Summary of Adverse Events
- TEAEs by SOC and PT
- TEAEs by SOC and PT, Related to Vaccination
- TEAEs by SOC and PT, Unrelated to Vaccination
- TEAEs by SOC, PT and Severity
- TEAEs by SOC, PT and Severity, Related to Vaccination
- TEAEs by SOC, PT and Severity, Unrelated to Vaccination
- TESAEs by SOC and PT
- TESAEs by SOC and PT, Related to Vaccination
- TESAEs by SOC and PT, Unrelated to Vaccination
- Listing of SAEs
- Listing of Related SAEs
- Listing of AEs

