7.8 Safety Evaluation

7.8.1 Adverse Events

The following analysis will be based on SS. The analysis of AEs for each vaccination of sIPV will be based on SS1_sIPV, SS2_sIPV, SS3_sIPV and the analysis of AEs for each vaccination of sIPV and

routine vaccines will be based on SS1_sIPV&Routine, SS2_sIPV&Routine, SS3_sIPV&Routine, respectively.

All AEs will be coded by using MedDRA 25.1 or later version, and be summarized by SOC and PT. This study focuses on the analysis of AEs occurring during the vaccination, which includes TEAEs occurring after (including) the first vaccination and within 28 days after the full vaccination. AEs which occurred before the first vaccination and 28 days after the full vaccination will be listed. AEs below are those that occurred during the vaccination if not otherwise specified.

The number of events, number of participants and percentage of participants reported the AEs will be calculated by groups (combined group C and combined group S), fisher's exact test will be used to test the differences between groups. The AEs will be summarized as following:

- ✓ All AEs;
- ✓ Vaccine-related AEs;
- ✓ Vaccine-unrelated AEs;
- ✓ AEs by severity (grade 1, grade 2, grade 3, grade 4, grade 5, \geq grade 2 and \geq grade 3);
- ✓ AEs by severity, related to vaccine;
- ✓ AEs by severity, unrelated to vaccine;
- ✓ AEs by onset time (30 minutes, 0-7 days, 8-28 days, 0-28 days, after 28 days);
- ✓ AEs by onset time, related to vaccine;
- ✓ AEs by onset time, unrelated to vaccine;
- ✓ AEs by doses;
- ✓ AEs by doses, related to vaccine;
- ✓ AEs by doses, unrelated to vaccine;
- ✓ AEs leading to early termination;
- ✓ AEs leading to early termination, related to vaccine.

Fisher's exact test will be used to compare the difference among groups.

When one participant experiences more than one AEs, he/she will be counted once to calculate the incidence, and the severest and most related events will be included when analyze the severity and relationship to the vaccine of AEs.

All AEs and AEs leading to early termination will be listed.

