7.8.2 Serious Adverse Events

The number of events, number of participants and percentage of participants reported the SAEs will be calculated by groups. Fisher's exact test will be used to compare the difference among groups. The SAEs will be summarized as following:

- ✓ All SAEs;
- ✓ Vaccination-related SAEs;
- ✓ Vaccination-unrelated SAEs.

All SAEs will be listed.

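### The SAP defines treatment emergence by start date alone, so a pre-vaccination condition that worsens after dose 1 and keeps its original date drops out of the AE summary tables

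*SAP*

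**What the plan says.** Protocol 9.3.5 gives a definition with two limbs: "Treatment-emergent adverse events (TEAEs) are defined as any AEs that occurred on or after vaccination date or worsening of existing events".

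SAP 7.1.2(2) replaces it with three rules based on dates:

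- On or after dose 1: "If the start date of AE is after (including) the date of the first vaccination, it will be defined as TEAE".
- Before dose 1: "If the start date of AE is before the date of first vaccination, it will be defined as non-TEAE".
- Date missing ("If either the start date of AE or the date of the first vaccination is missing") and timing therefore unclear: the event is counted as a TEAE.

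SAP 7.8.1 restricts its summaries to TEAEs between the first vaccination and 28 days after full vaccination ("AEs below are those that occurred during the vaccination if not otherwise specified"). For the rest it says: "AEs which occurred before the first vaccination and 28 days after the full vaccination will be listed". SAP 7.8.2 has its own text for serious events and does not mention treatment emergence: "The number of events, number of participants and percentage of participants reported the SAEs will be calculated by groups". SAP 2.3 declares no departure from the protocol.

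**The concern.** The SAP narrows a protocol definition without saying so, and on this limb the change can only take events out of the tables. Safety is a co-primary objective here, so a documented aggravation after vaccination is an event a reader would expect to find in the summaries, particularly if it reaches grade 3. The SAP is also uneven in its caution. An event whose timing is unknown is counted as treatment-emergent, while an event known to have worsened after vaccination is not, if its recorded start is earlier.

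**Working it through.** There is no figure in the plan to reproduce. The check is to apply each definition to the possible cases and follow the result to the output.

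| Case | Protocol 9.3.5 | SAP 7.1.2(2) | Result in SAP 7.8.1 |
|---|---|---|---|
| (a) Starts before dose 1, worsens after it, original start date kept | TEAE | non-TEAE | Listing only |
| (b) As (a), but the worsening is entered as a new AE with its own date | TEAE | TEAE | Tabulated |
| (c) Starts after dose 1, worsens after a later dose | TEAE | TEAE | Tabulated |
| (d) Start date missing, timing unclear | Not addressed | TEAE | Tabulated |

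The SAP loses an event that the protocol counts in case (a) only.

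In case (a) the event misses each kind of 7.8.1 summary, for three reasons:

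1. The all-AE and severity summaries are confined to TEAEs.
2. SAP 7.1.2(3) defines relatedness for TEAEs only, so the vaccine-related summaries do not take it up.
3. SAP 7.1.2(1) sets onset time as start date minus vaccination date. For a start before dose 1 this is negative, and none of the 7.8.1 onset bands begins below day 0.

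Whether (a) or (b) applies depends on data entry. Protocol 8.2 requires relevant changes during the study to be recorded on the AE page. Neither document says whether a worsening takes a new start date or stays under the old one.

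For scale, SAP 7.1.5 pools the groups for safety, so each combined group has 360 + 360 = 720 infants. The documents give no baseline morbidity. As an illustration only, assume that 2% to 5% have an ongoing mild condition at Visit 1 and that 10% to 30% of those worsen after a dose:

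- Low: 720 × 0.02 × 0.10 = 1.4 infants (1.4 / 720 = 0.2%).
- High: 720 × 0.05 × 0.30 = 10.8 infants (10.8 / 720 = 1.5%).

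Both figures suppose that every such record keeps its original date and make no allowance for the exclusion criteria, so under those rates they are ceilings.

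**The case against.** The best defence is that case (a) should hardly arise. Protocol 8.5.1 ties an AE to a participant who has been vaccinated, and the diary in 8.5.5 starts at the first vaccination. Medical history is collected separately and has its own table in SAP 7.4. A baseline condition would then be history, and its worsening a new AE dated after dose 1, which the SAP does count. Exclusion criteria 15 and 16 remove infants with acute illness in the previous 7 days or an axillary temperature of 37.3°C or more, and screening on the day of vaccination is recommended.

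Most of this stands as an argument about frequency. It does not remove the contradiction: the SAP itself foresees AEs dated before vaccination, since it has a rule and a listing for them, and nothing fixes the date that a worsening takes.

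A reader might go further than the documents allow in three ways:

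- **That aggravated conditions vanish from every safety table.** SAP 7.8.2 tabulates serious events with no TEAE limit of its own, and it is unclear whether the scope sentence in 7.8.1 reaches it. The events also remain in a listing.
- **That the primary 7-day adverse reaction endpoint is shown to be biased.** Solicited symptoms are recorded daily on a card that starts at vaccination. The rule is the same for both combined groups, so no between-group bias follows from it.
- **That events are assigned to the wrong dose or vaccine.** An event that starts after one dose and worsens after another is a TEAE under both documents. The protocol has no rule that dates onset at worsening, the SAP refers only to the corresponding vaccination, and the staggered groups get a new diary card at each vaccination visit. The lack of a dating rule is a separate gap and contradicts nothing in the protocol.

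**Conclusion.** The contradiction is certain. The SAP drops the protocol's worsening limb, does so in the non-conservative direction, and declares consistency all the same. The consequence is conditional: a worsened pre-vaccination condition leaves the SAP 7.8.1 summaries only if its record keeps a start date before dose 1.

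The number affected cannot be derived from the documents. It is probably small, given criteria 15 and 16, and the 1 to 11 infants per combined group shown above rest entirely on assumed rates. An effect on the SAE tables is not established. The point merits correction because a single related event of grade 3 or higher can matter and the repair is cheap.

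**What to change.** - **SAP 7.1.2(2):** add that an AE starting before the first vaccination which increases in severity or becomes serious on or after that date is a TEAE, with the date of worsening as its onset. A worsening entered as a new AE record with its own start date already meets this.
- **SAP 7.8.2:** state whether the SAE tables are limited to TEAEs. Protocol 9.3.5 plans tables of treatment-emergent SAEs, so the reader needs to know which set is shown.
- **SAP 2.3:** if the narrower definition is intended, declare and justify it here instead of stating consistency.

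The cost is a sentence or two in the SAP, a small change to the TEAE derivation and a slightly higher AE count. The derivation needs a date and grade for each worsening. If the eCRF did not capture them, the SAP should say so as a limitation.

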7.1.3 The Window of Analysis

For visits after baseline, all analysis will be conducted based on the scheduled visits in the protocol. The unscheduled visits will not be included in the summary tables, but will be listed.

7.1.4 Analysis Software

All statistical analysis will be conducted by SAS 9.4 or later version.

7.1.5 Table and Listings

- **Tables**

Excluding safety evaluation, all data will be summarized by group (i.e., C1, C2, S1 and S2). In safety evaluation, the data will be summarized by combined group C (including C1 and C2) and combined group S (including S1 and S2).

➤ **Listings**

Unless otherwise specified, listings generally include participant ID and group. Study Data Tabulation Model (SDTM) data is preferred to display in the listing. They will be sorted by group, participant ID, visit or other relevant time (e.g., start date of AE).

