(3) Safety Set (SS): All randomized participants who completed at least one dose vaccination will be included in the safety set. Participants who are vaccinated with the wrong vaccine will be analyzed for safety evaluation as treated according to All Subjects as Treated (ASaT) principle.

(4) Safety Set 1 for sIPV (SS1_sIPV) : All randomized participants who completed the 1st vaccination of sIPV will be included in SS1_sIPV. Participants who are vaccinated with the wrong

vaccine will be analyzed for safety evaluation as treated according to ASaT principle.

(5) Safety Set 2 for sIPV (SS2_sIPV): All randomized participants who completed the 2nd vaccination of sIPV will be included in SS2_sIPV. Participants who are vaccinated with the wrong vaccine will be analyzed for safety evaluation as treated according to ASaT principle.

(6) Safety Set 3 for sIPV (SS3_sIPV): All randomized participants who completed the 3rd vaccination of sIPV will be included in SS3_sIPV. Participants who are vaccinated with the wrong vaccine will be analyzed for safety evaluation as treated according to ASaT principle.

(7) Safety Set 1 for sIPV and routine vaccines (SS1_sIPV&Routine): All randomized participants who completed 1st vaccination of sIPV and routine vaccines will be included in SS1_sIPV&Routine. Participants who are vaccinated with the wrong vaccine will be analyzed for safety evaluation as treated according to ASaT principle.

(8) Safety Set 2 for sIPV and routine vaccines (SS2_sIPV&Routine): All randomized participants who completed 2nd vaccination of sIPV and routine vaccines will be included in SS2_sIPV&Routine. Participants who are vaccinated with the wrong vaccine will be analyzed for safety evaluation as treated according to ASaT principle.

(9) Safety Set 3 for sIPV and routine vaccines (SS3_sIPV&Routine): All randomized participants who completed 3rd vaccination of sIPV and routine vaccines will be included in SS3_sIPV&Routine. Participants who are vaccinated with the wrong vaccine will be analyzed for safety evaluation as treated according to ASaT principle.

7 Statistical Method

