7.10 Subgroup Analysis

Subgroup analysis is planned for both immunogenicity evaluation and safety evaluation in participants of different study country (including Bangladesh and Pakistan).

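### The pooled 0-7 day safety rows test three post-dose windows in combined group C against six in combined group S, so background events tilt their p-values towards co-administration

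*SAP*

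**What the plan says.** - **Groups.** SAP 7.1.5: "In safety evaluation, the data will be summarized by combined group C (including C1 and C2) and combined group S (including S1 and S2"). SAP 7.8.1 repeats that event counts and percentages "will be calculated by groups (combined group C and combined group S").
- **Test.** SAP 7.8.1 states that Fisher's "exact test will be used to test the differences between groups".
- **Rows.** SAP 7.8.1 lists "AEs by onset time (30 minutes, 0-7 days, 8-28 days, 0-28 days, after 28 days") for all AEs, and again for vaccine-related and unrelated AEs.
- **Counting.** "When one participant experiences more than one AEs, he/she will be counted once to calculate the incidence" (SAP 7.8.1).
- **Clock.** SAP 7.1.2 measures onset from "the corresponding vaccination date".
- **Visits.** Protocol 8.6.1 gives group C three vaccination visits; Protocol 8.6.2 gives group S six. Protocol 8.5.1 opens a Day 0 to 7 solicited period after each.
- **Per-dose sets.** SAP section 6 defines SS1 to SS3_sIPV by sIPV dose. For the paired sets it says "All randomized participants who completed 1st vaccination of sIPV and routine vaccines will be included in SS1_sIPV&Routine", and likewise for doses 2 and 3. It does not say which days those sets count.
- **Country.** "Subgroup analysis is planned for both immunogenicity evaluation and safety evaluation in participants of different study country (including Bangladesh and Pakistan") (SAP 7.10).
- **Endpoint.** The primary safety endpoint in Protocol 3 is the incidence of adverse reactions in the 7 days after each dose. SAP 5.2 and 7.8.1 do not say which table reports it.

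**The concern.** An infant in S has six chances to record an event within 7 days of a vaccination; an infant in C has three. An unrelated fever two weeks after the first visit falls in the 0-7 day row in S, because the second vaccination has just been given. In C it does not. The count is of infants with at least one event, so more windows mean a higher percentage even if the vaccines do nothing.

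The extra reactions that a vaccine causes at an extra visit are a real feature of the staggered schedule. Only the background part is an artefact. It favours co-administration, on the subject of the primary safety objective. It can produce a significant difference where none exists, and it can offset a true excess at co-administered visits.

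**Working it through.** The plan gives no safety sample size, background rate or reaction rate, so there is no figure of its own to reproduce.

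**Inputs from the documents.** Each group has 360 infants (SAP 4.3), so each combined group has 2 × 360 = 720. Windows: 3 in C, 6 in S. Every infant is due three sIPV doses and three routine-vaccine visits.

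**Assumptions.** Background probability b per window is the same in both arms and independent across windows. A share f of background is counted in the row: f = 1 for all AEs, and f below 1 for adverse reactions. Reaction probabilities are rs per sIPV dose and rr per routine dose. Fisher's test is two-sided at 0.05 (the SAP states no level), with no dropout.

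**Formulas.** With q = (1−rs)³(1−rr)³:

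- C = 1 − (1−fb)³ q
- S = 1 − (1−fb)⁶ q

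Example, b = 2%, f = 1, rs = 3%, rr = 15%: q = (0.97 × 0.85)³ = 0.5605. C = 1 − 0.98³ × 0.5605 = 47.2% and S = 1 − 0.98⁶ × 0.5605 = 50.3%.

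**Chance of p<0.05 favouring C**, summed exactly over both binomial distributions:

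| b per window | No reactions, f = 1: C vs S | Chance | 3%/15%, f = 1: C vs S | Chance | 3%/15%, f = 25%: chance |
|---|---|---|---|---|---|
| 0.5% | 1.5% vs 3.0% | 40.3% | 44.8% vs 45.6% | 4.5% | 2.7% |
| 1% | 3.0% vs 5.9% | 72.7% | 45.6% vs 47.2% | 7.9% | 3.2% |
| 2% | 5.9% vs 11.4% | 95.9% | 47.2% vs 50.3% | 19.7% | 4.5% |
| 5% | 14.3% vs 26.5% | >99.9% | 51.9% vs 58.8% | 72.9% | 10.2% |

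With equal windows the chance in this direction is about 2% or less. For adverse reactions the no-reaction column is an upper bound.

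**Sensitivity.**

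- Reactions of 5%/30%, f = 1: 3.3%, 4.9%, 9.3%, 34.1%. With f = 25%: 2.4%, 2.7%, 3.3%, 5.8%.
- Within-infant correlation of 0.2 in background, f = 1: 14%, 30%, 57%, 92% without reactions, and 3%, 4%, 8%, 26% with 3%/15%.
- A less frequent term (0.5% per sIPV dose, 1% per routine dose) at b = 2%: 10.0% vs 15.3%, chance 84% at f = 1 but 16% at f = 25%.

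**Masking.** An added risk x per co-administered visit gives C = 1 − (1−fb)³(1−x)³ q, which equals S when x = fb. With x = fb = 2% and 3%/15%, both arms are 50.3%. The chance of detecting the excess is 2.1%, against 19.7% if the background windows were equal (50.3% vs 47.2%).

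**Paired sets.** If SSn_sIPV&Routine counts both S visits, it compares one window with two. At b = 5%, f = 1: 5.0% vs 9.75% without reactions (chance 92%), and 21.7% vs 25.6% with 3%/15% (39%).

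**Vaccine content of the per-dose comparisons**, at fb = 2% and 3%/15% with no interaction:

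- After an sIPV dose: C = 1 − 0.98 × 0.97 × 0.85 = 19.2%; S = 1 − 0.98 × 0.97 = 4.9%. This is significant against C in practically every trial.
- After a routine-vaccine visit: C = 19.2%; S = 1 − 0.98 × 0.85 = 16.7%.

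**Onset rows beyond day 7.** Protocol 8.5.1 gives S a Day 8-14 unsolicited period after every dose but the last. The 8-28 and 0-28 day rows therefore match S only after its sixth dose.

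**The case against.** **Causality limits the adverse-reaction row.** Protocol Table 6 classes events with another plausible explanation as unlikely or not related, and SAP 7.1.2 counts both as unrelated. This stands. A reader might infer that the reaction row is distorted as much as the all-AE row; the documents do not support that. If a quarter of background is judged related, 2% related background means 8% in total (2% / 0.25). But the row is not immune: Table 6 allows a possible rating for events that concurrent illness could also explain, and the SAP counts those as related.

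**Equal-window tables are already planned.** The SS1 to SS3_sIPV tables compare one window with one. This also stands. However, the SAP text does not link them to the primary endpoint, and they leave the pooled Fisher rows in place. The mock shells, which are not among the documents, may supply the link. Nor can these tables carry the endpoint alone: they set sIPV plus routine vaccines against sIPV alone. No planned set isolates the routine-vaccine visits of S.

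**Safety is descriptive.** SAP 7.6 contains no safety hypothesis. This limits the consequence, but the SAP still orders p-values on these rows and repeats the comparison by country.

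**Whole-follow-up totals are not doubled.** A reader might extend the three-to-six imbalance to total AEs and SAEs. Nominal follow-up is 3 × 28 = 84 days in C and 5 × 14 + 28 = 98 in S, a much smaller difference, although prompted recording of solicited events still runs only after each dose.

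**Conclusion.** The point holds for the pooled 0-7 day AE and adverse-reaction rows, including their SOC/PT and country breakdowns. For the paired sIPV-and-routine sets it holds only if both S visits are counted. The direction follows from the design whenever some background is counted. The size rests on assumed background, reaction rates and relatedness. It is large for the all-AE row when background is high relative to reactions, and small for overall adverse reactions unless related background reaches about 2% per window.

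A reader might infer that the primary safety conclusion is bound to favour co-administration. The documents do not support that: they name no table for that endpoint, plan some equal-window tables, and rest no success criterion on a safety p-value. The realistic harm is a misleading tolerability statement, which is minor to moderate.

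**What to change.** 1. In SAP 7.8.1, present the cumulative 0-7 day C versus S rows descriptively, without Fisher p-values, and state the number of windows per arm. Apply this to AEs and adverse reactions, to the SOC/PT and country breakdowns, and to SSn_sIPV&Routine if both S visits count.
2. Add SS1 to SS3_Routine sets for days 0-7 after each routine-vaccine visit: pooled C versus S, with C2 versus S2 as the age-matched version. Keep SS1 to SS3_sIPV, with C1 versus S1 as the age-matched version.
3. Report the primary adverse-reaction endpoint from both per-dose sets together, not from the sIPV sets alone. Beside each table, state which vaccines each arm received at that visit. One set compares sIPV plus routine vaccines with sIPV alone; the other compares routine vaccines plus sIPV with routine vaccines alone.
4. State which days SSn_sIPV&Routine counts, and reconcile the 8-28 and 0-28 day rows with the Day 8-14 period in Protocol 8.5.1.

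**Cost.** SAP wording, a few more tables from data already collected, and fewer p-values. C2 versus S2 has 360 per arm and is less precise. For an illustrative 18.4% vs 15.8%, the 95% CI half-width is 1.96 × √(0.184 × 0.816/360 + 0.158 × 0.842/360) = 5.5 percentage points, against 3.9 at 720 per arm.

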4. STUDY DESIGN

4.1 Overall Design

This is a multi-country multi-center study, and the enrollment plan will be specified in each country.
The study protocol will be adjusted based on local conditions and requests from local IRB/IEC.

This is a multi-country, multi-center, open-labelled, randomized, controlled, extended phase III clinical trial. Totally 1440 healthy infants of 6 weeks old (42-47 days) for Bangladesh and of 6-8 weeks old (42-56 days) for Pakistan are planned to be enrolled, and then randomized in a 1:1:1:1 ratio into four groups, i.e., co-administration group 1 (group C1), co-administration group 2 (group C2), staggered administration group 1 (group S1) and staggered administration group 2 (group S2). Participants in group C1 and C2 will receive sIPV at 6,10, 14 weeks old (at 4-week intervals), administered concomitantly with routine infant vaccine (may include DTP-HepB-Hib vaccine, PCV or rotavirus vaccine in accordance with the local routine vaccination schedule). Participants in group S1 will receive sIPV at 6,10,14 weeks old, and receive routine infant vaccines at 8,12,16 weeks old (at 4-week intervals, respectively). Participants in group S2 will receive routine infant vaccines at 6,10,14 weeks old, and receive sIPV at 8,12, 16 weeks old (at 4-week intervals, respectively).

For all the participants, the immediate reactions within 30 minutes after each dose of vaccination will be observed on site. Guardians of participants will utilize the diary card to record solicited adverse events from the time of vaccination for 7 days post-vaccination of each dose. From the time of the first vaccination and 28 days post-vaccination of the last dose, unsolicited adverse events and any SAEs will be required to be recorded in the diary card.

About 3 ml venous blood will be collected before the first vaccination and 28 days (+7) after the last vaccination of sIPV or routine vaccines. Antibodies level will be determined using the collected sera for immunogenicity evaluation. The antibody testing required for each group is shown in Table 4. Group C1 and S1 will be compared in terms of immunogenicity against polio; Group C2 and S2 will be compared in terms of immunogenicity against diphtheria, Tetanus, Pertussis, Hepatitis B, Hib and Pneumococcal.

Table 4 Study Design

Group Code	Sample size	Vaccination schedule						Antibody tests	
		6 weeks	8 weeks	10 weeks	12 weeks	14 weeks	16 weeks	Blood collection time	Testing item

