4.2 Rationale for Study Design

This study is designed to study the immunogenicity and safety of sIPV co-administered with other routine infant vaccines. According to the national immunization schedule of Bangladesh and Pakistan, sIPV was administered concomitantly with PCV, DTP-HepB-Hib and other vaccines at 6, 10 and 14 weeks old. Thus, this study set up the concomitant vaccination schedule according to the real practice in study area. The primary hypothesis of this study is that the seroconversion rate of polio vaccination when administered concomitantly with routine vaccines is non-inferior to that of being administered alone. The secondary hypothesis is that the sero-protection rates of diphtheria, tetanus, and the seropositivity rate of pertussis when routine vaccines are administered concomitantly with sIPV are non-inferior to those administered without sIPV. Two staggered administration groups were designed in this study, one is administered with sIPV at 6 weeks old as the comparator for the non-inferiority evaluation of immune response to polio; another is administered with routine infant vaccines at 6 weeks old, as the comparator for the non-inferiority evaluation of immune response to diphtheria, tetanus, and pertussis. In that way, effects of age on the immune response after vaccination are avoided.

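### The planned adverse-event tables do not show how much reactogenicity sIPV adds to the routine visit, although the randomisation allows it through C versus S2

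*SAP*

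**What the plan says.** Protocol 3 makes adverse reactions in the 7 days after each dose a primary endpoint. Protocol 4.1 has C1 and C2 receive sIPV and routine vaccines together at 6, 10 and 14 weeks. S1 receives sIPV at those ages and routine vaccines two weeks later. S2 is the reverse: "Participants in group S2 will receive routine infant vaccines at 6,10,14 weeks old, and receive sIPV at 8,12, 16 weeks old".

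The SAP reports non-safety data by the four arms, but for safety: "In safety evaluation, the data will be summarized by combined group C (including C1 and C2) and combined group S (including S1 and S2"). SAP 7.8.1 repeats this for adverse events: counts and percentages "will be calculated by groups (combined group C and combined group S"), with Fisher's exact test. SAP 7.8.2 on serious events is less specific: "The number of events, number of participants and percentage of participants reported the SAEs will be calculated by groups".

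SAP 6 defines an overall safety set and two dose-level families. One is for sIPV: "All randomized participants who completed the 1st vaccination of sIPV will be included in SS1_sIPV". The other is for both components: "All randomized participants who completed 1st vaccination of sIPV and routine vaccines will be included in SS1_sIPV&Routine". Each runs to the third dose. No set is defined by receipt of a routine dose alone. The only planned safety subgroup is country (SAP 7.10).

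**The concern.** S1 and S2 are separate randomised arms that receive different products at every visit. For immunogenicity the protocol keeps them apart so that each question has a same-age control; Protocol 4.2 says "In that way, effects of age on the immune response after vaccination are avoided". For adverse events the SAP merges them.

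At the 6-week visit C and S2 are randomised, of the same age and given the same routine vaccines, with one 7-day window each. They differ only in whether sIPV is also given. That is the direct measure of the reactogenicity sIPV adds to a routine visit, which a programme adding sIPV would want to know. Nothing in the SAP text tabulates S2 separately or isolates the routine-alone visits, so the figure would be missing from the main report.

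The dose-level sets have a related gap. An S2 infant who stops vaccination after the first routine dose, before any sIPV, enters neither SS1_sIPV nor SS1_sIPV&Routine. A C infant who stops after the same visit has received both components and enters both sets.

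**Working it through.** **The plan's own figure.** None is given for safety. The only calculation is the polio non-inferiority size of 233 per group (90% in both arms, margin 10 points, one-sided 0.025, power 93.3%). A Farrington–Manning score test needs 232, with 93.5% power at 233, so the figure reproduces. This point does not affect it.

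**Inputs.** 360 per arm (SAP 4.3), so C = 720, S2 = 360 and pooled S = 720. The documents give no reaction rates, so all rates below are assumptions.

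**What each comparison estimates.** Three scenarios for the 7-day reaction rate:

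- A: 10% after sIPV alone, 20% after routine alone, independent, so C = 1 − 0.90 × 0.80 = 28%.
- B: 10% after sIPV alone, 40% after routine alone, 45% after both.
- N: as B, but C = 40%, so sIPV adds nothing.

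For SS1_sIPV&Routine, I count an S infant as reacting if there is a reaction in either of its two windows, assumed independent: 1 − 0.80 × 0.90 = 28% in A and 1 − 0.60 × 0.90 = 46% in B and N.

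| Comparison | A | B | N |
|---|---|---|---|
| C − S2, 6-week visit | 28 − 20 = +8 | 45 − 40 = +5 | 40 − 40 = 0 |
| C − pooled S, SS1_sIPV | 28 − 10 = +18 | 45 − 10 = +35 | 40 − 10 = +30 |
| C − pooled S, SS1_sIPV&Routine | 28 − 28 = 0 | 45 − 46 = −1 | 40 − 46 = −6 |

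Row 2 estimates the effect of adding routine vaccines to sIPV, with the S infants at 6 weeks (S1) or 8 weeks (S2). Row 3 compares one combined visit with two separate visits. Only row 1 estimates what sIPV adds to the routine visit.

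Over the whole series in scenario A, both strategies give 1 − 0.72³ = 62.7%, a difference of 0, because every S infant eventually receives the same vaccines.

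**Precision of C versus S2.** The half-width is 1.96 × √[p(1−p)(1/720 + 1/360)]. With equal rates:

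| Assumed rate | C vs S2 (720 vs 360) | C vs pooled S (720 vs 720) |
|---|---|---|
| 10% | 3.8 points | 3.1 points |
| 20% | 5.1 | 4.1 |
| 30% | 5.8 | 4.7 |
| 40% | 6.2 | 5.1 |

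The smallest increase detectable with 80% power (two-sided 0.05) is about 6.2, 7.8, 8.7 and 9.0 points at S2 rates of 10%, 20%, 30% and 40%. For 50% versus 40%, SE = √(0.50 × 0.50/720 + 0.40 × 0.60/360) = 0.0318 and power = Φ(0.10/0.0318 − 1.96) ≈ 88%. If the full 15% dropout fell before this window (612 versus 306), SE = 0.0318/√0.85 = 0.0345 and power ≈ 83%.

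**The case against.** The strongest reply is that the pooled tables are not wrong. Pooled C versus S compares co-administration with staggering over the series, and SS1_sIPV compares sIPV with and without same-visit routine vaccines, which is close to the trial's title. SAP 7.6 states no comparative safety hypothesis. This stands: C versus S2 is a further question, to be added alongside the pooled comparison.

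Several stronger readings are tempting but are not supported:

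- *sIPV is the only difference at all three rounds.* This holds only at 6 weeks. By 10 and 14 weeks S2 has received sIPV about two weeks earlier, whereas C received its previous sIPV four weeks earlier together with routine vaccines.
- *The contrast should use adverse reactions.* Protocol 8.5.1 defines these against the experimental vaccine, Table 6 grades causality against the investigational product, and Protocol 6.1 lists only sIPV as experimental. On that reading an S2 infant at 6 weeks, not yet given sIPV, cannot have a reaction, and C would show an artificial excess. Protocol 2.3.1 and 6.7 use the term study vaccine more broadly, so the attribution rule is unclear.
- *The S rows mix sIPV-alone and routine-alone visits by visit number.* The SAP ties by-dose analysis to sIPV dose or sIPV-and-routine dose. No visit-number set exists.
- *Every safety table is pooled.* SAP 7.8.2 says only that serious events are shown by group; pooling there rests on the general rule in 7.1.5. The mock-up shells are not available.
- *A two-week age difference is known to matter for reactions.* Protocol 4.2 speaks only of immune response.

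It can also be said that listings carry the group, so the contrast is recoverable. That is true, but SAP 2.2 keeps additional analyses out of the final study report, and the contrast would then be chosen after the data are seen.

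**Conclusion.** The point holds as a gap in what the SAP text reports. Adverse events are shown only by combined C and combined S, no safety set is based on routine doses, and no described table gives the increment of sIPV over the routine visit. On the assumed rates that increment can be +5 to +8 points while the both-component comparison reads −1 to 0 and the sIPV-dose comparison reads +18 to +35. These sizes depend entirely on the assumed rates and, in part, on independence.

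A reader might infer that the pooled analysis is invalid or that a safety signal will be hidden. The documents do not support that: the pooled tables answer other legitimate questions and the data remain in the listings. This is an inexpensive improvement to the reporting of a primary safety objective. It does not affect the sample size or the immunogenicity analysis.

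**What to change.** - In SAP 7.1.5 and 7.8, show adverse-event and serious-event tables as C, S1, S2 and total S, keeping the pooled C versus S comparison.
- In SAP 6, add SS1_Routine to SS3_Routine: participants who completed the first, second or third routine vaccination.
- In SAP 7.8.1, add the site-stratified C minus S2 difference with 95% CI at the 6-week visit, for any solicited event, any adverse event and any event of grade 3 or higher within 7 days, regardless of attributed causality. Label it as the effect of adding sIPV to the first routine visit.
- Report rounds 2 and 3 in the same form but descriptively, noting S2's sIPV dose about two weeks before.
- Use vaccine-related events in this contrast only if the SAP states that causality is assessed against any vaccine given in the study, including the routine vaccines.
- Show S1 at 6, 10 and 14 weeks descriptively as the same-age sIPV-alone profile.
- Label the intervals as estimates without multiplicity adjustment.

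The cost is SAP text, three derived sets and a few extra columns, with no new data or participants. The S2 comparator has 360 infants instead of 720, so the interval is wider: about ±6.2 instead of ±5.1 points at an assumed 40% rate.
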